A participant account in a secure web portal will be created with a username (user email addresses) and a temporary password. Potential participants will log in to the portal and will be instructed to change their password. In the portal, potential participants will complete two forms needed to determine eligibility: the PHQ-8 and the Medication Use Screener (see Appendix 1). Potential participants who do not meet criteria for participation based on the PHQ-8 (score < 5) or who do not wish to (or cannot) respond to the Medication Use Screener will be informed of their ineligibility and directed to mental health resources.

Participants and legal guardians (if applicable) will then be asked to verbally confirm that they meet each eligibility criterion. To ensure privacy, legal guardians will be asked to leave the room unless the participant indicates that they want their guardian present. After confirming eligibility with the participant, the legal guardian will be asked to return and confirm the eligibility of their child. Participants who report a history of suicidal ideation or self-harm urges will be prompted to complete a safety plan in collaboration with the research coordinator and/or study clinician (Appendix 5). If participants endorse active suicidal ideation with intent during this session, they will be directed to seek an emergency psychiatric evaluation for further assessment of their risk and appropriate intervention (see section 4.8.1). Participants (or legal guardians) who indicate ineligibility to participate due to any of the other eligibility criteria will be directed to alternative mental health resources and will be ineligible to continue with participation. Participants who are ineligible as a result of having an incompatible mobile device/operating system will be sent an email offering the opportunity to schedule another video session if their device/operating system changes. All eligible participants will be provided with a safety plan document and instructions for completing and using this safety plan document should it be necessary (Appendix 5). An emailed or text reminder to complete this plan may be sent following the consent session.

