3.4 Assessments

The following Prescreening, Baseline, post-intervention, and follow-up assessments will be completed via secure web portal. Weekly participant assessments (PHQ-8, PSC) will be completed in the mobile app. Weekly legal guardian assessments (PHQ-8, PSC proxies) will be completed via the secure web portal. All assessments are provided in Appendix 1, with the exception of the Prescreening Questionnaire (Appendix 3).

Table 1. Schedule of Assessments					
	Eligibility Screening	Baseline	Weekly during intervention period	Post-intervention	1-month follow-up (4 weeks post intervention)
Prescreening Questionnaire	X (if used)				
Patient Health Questionnaire (PHQ-8)	X		X	X	X
Medication Use Screener	X				
Baseline Questionnaire		X			
Baseline Questionnaire, legal guardian proxy*		X			
Patient Health Questionnaire (PHQ-8, legal guardian proxy*)		X	X	X	X
Behavioral Activation for Depression Scale - short form (BADS)		X		X	X
Generalized Anxiety Disorder (GAD-7)		X		X	X
Pediatric Quality of Life Enjoyment & Satisfaction Questionnaire (PQ-LES-Q)		X		X	X
Pediatric Quality of Life Enjoyment & Satisfaction Questionnaire (PQ-LES-Q, legal guardian proxy*)		X		X	X
Participant Symptom Check (PSC)			X	X	X

Participant Symptom Check (PSC, legal guardian proxy*)			X	X	X
Post-Intervention Questionnaire				X	
Post-Intervention Questionnaire, legal guardian*				X	
Systems Usability Scale (SUS)				X	
User Engagement Scale (UES-SF)				X	
1 month follow-up Questionnaire					X
1 month follow-up Questionnaire, legal guardian*					X
Absenteeism Questionnaire		X		X	X
Healthcare Utilization Questionnaire		X		X	X
Absenteeism Questionnaire, legal guardian*		X		X	X
Healthcare Utilization Questionnaire, legal guardian*		X		X	X

* Only administered when participants are under 18 years of age

Description of Assessments

- The **Prescreening Questionnaire** is administered to potential participants on the study website landing page and assesses whether or not participants are preliminarily eligible to participate based on yes/no/unsure responses to clustered sets of eligibility criteria (Appendix 3).

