- The **Patient Health Questionnaire (PHQ-8) Participant and Legal Guardian Proxy** is an 8-item participant-report measure for screening for depression and for establishing depression severity¹⁰⁰. The total score ranges from 0-24, with a higher score indicating greater depression symptom severity. For participants under 18, a legal guardian proxy version of the PHQ-8 will be administered to legal guardians. Clinically significant improvement is defined as a reduction in assessment score ≥ 5 ¹⁰¹. Intervention response is defined as 50% reduction in symptoms from pre- to post-intervention, and remission is defined as a score < 5 following intervention¹⁰².
- **Medication Use Screener** is a single-item screening form that asks participants to report whether or not (yes/no) they are currently taking psychotropic medication for the treatment of depression or symptoms of depression.
- **7 item Generalized Anxiety Disorder scale (GAD-7)**. The GAD-7 is a validated 7-item participant-reported assessment for generalized anxiety disorder¹⁰³. We will evaluate changes in anxiety symptoms given the high comorbidity between anxiety and depression. The total score ranges from 0-21, with a higher score indicating greater anxiety symptom severity.
- **Pediatric Quality of Life Enjoyment & Satisfaction Questionnaire (PQ-LES-Q) Participant & Legal Guardian**: A 15-item participant-reported self-administered questionnaire that captures life satisfaction over the past week¹⁰⁴. Each question is rated on a 5-point scale from 1 (Very Poor) to 5 (Very Good). The first 14 items are summed to form a total score ranging from 14-84, with higher scores indicating higher quality of life. The 15th item ("Overall, how has your life been?") is a stand-alone item. For participants under 18, a legal guardian proxy version of the PQ-LES-Q will also be administered to legal guardians.
- **Participant Symptom Check (Participant and Legal Guardian)**. Assesses legal guardian- and participant- reported negative symptoms and changes in treatment since the last check-in, using multiple choice and free-form text responses.

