- **Behavioral Activation for Depression Scale - Short Form (BADS)**. The BADS¹⁰⁵ consists of 9 participant-reported questions assessing behavioral activation and avoidance over the previous week, each rated on a 7-point scale ranging from 0 (not at all) to 6 (completely). This form can be used to track behaviors hypothesized to underlie depression and specifically targeted for change by behavioral activation. It examines changes in the following areas: activation, avoidance/rumination, work/school impairment, and social impairment. The total score ranges from 0 to 54, with higher scores indicating higher activation.
- **Baseline Questionnaire (Participant and Legal Guardian)**. This participant- and legal guardian-reported questionnaire includes participant age, sex, gender, socio-economic status, medical

history, and medications.

- **Post-Intervention Questionnaire (Participant and Legal Guardian).** This participant- and legal guardian-reported questionnaire assesses feedback on the mobile app.
- **System Usability Scale (SUS).** The SUS¹⁰⁶ is a participant-reported scale that provides a quick, reliable tool for measuring the usability of the mobile app. The SUS consists of a 10-item questionnaire with five response options for respondents, ranging from Strongly Agree to Strongly Disagree. The total score ranges from 0-100, with higher scores indicating greater usability.
- **User Engagement Scale - Short Form (UES-SF).** The UES-SF¹⁰⁷ is a participant-reported, statistically reliable measure of self-reported user engagement that is tailored to the specific device being tested (i.e., the study app). The form has 12 items and uses a 5-point Likert scale. There are 4 subscales: Aesthetic appeal, focused attention, perceived usability, and reward. Each subscale score ranges from 1-5, with higher scores indicating higher levels of each scale. The total score also ranges from 1-5, with higher scores indicating more engagement.
- **One month follow-up Questionnaire (Participant and Legal Guardian).** This participant- and legal guardian-reported questionnaire assesses feedback on the mobile app.
- **Absenteeism Questionnaire (Participant and Legal Guardian)** This participant- and legal guardian-reported questionnaire assesses missed time at work and/or school attributable to the participant's mental health condition over the past 4 weeks.

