4.5 Safety Outcomes

- Number of adverse events (AEs), number of participants with AEs, and rates of AEs based on

- PHQ-8-based symptom deterioration and responses to weekly PSC questionnaires (both groups)
- Number of AEs, number of participants with AEs, and rates of AEs based on in-app freeform text (SparkRx group only)
- Number of adverse device effects (ADEs), number of participants with ADEs, and rates of ADEs (SparkRx group only)

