PIs along with the Medical Expert and study clinicians will provide continuous, close monitoring of all reported adverse events (AEs) and adverse device effects (ADEs). In compliance with IRB and DSMB guidelines, investigators will report adverse events and adverse device effects as required.

An adverse event is defined as any unwanted medical occurrence that occurs during the study. An adverse device effect (ADE) is an adverse event related to the use of an investigational medical device. This includes any adverse event resulting from insufficiencies or inadequacies in the instructions for use, the deployment, the installation, the operation, or any malfunction of the investigational medical device. This also includes any event that is a result of a user error or intentional misuse.

For this study, ADEs may occur in only the SparkRx arm.

An adverse event or adverse device effect is considered serious if it meets any of the following criteria:

- Is fatal;
- Is life-threatening, meaning, the participant was, in the view of the investigator, at immediate risk of death from the reaction as it occurred;
- Leads to persistent or significant disability/incapacity, i.e., the event causes a substantial disruption of a person's ability to conduct normal life functions;
- Requires or prolongs inpatient hospitalization;
- Is an important medical event, based on appropriate medical judgment, that may jeopardize the participant, or the participant may require medical or surgical intervention to prevent one of the other outcomes above.
 - Note 1: Planned hospitalization for a pre-existing condition, or a procedure required by the investigational protocol, without serious deterioration in health, is not considered a serious adverse event.
 - Note 2: Serious adverse device effect (SADE): adverse device effect that has resulted in any of the consequences characteristic of a serious adverse event.

The degree of certainty of causal relationship of an ADE to the mobile investigational device will be rated as follows:

- Not Possible: An event that is not due to the use of the study device. An alternative explanation, e.g., concomitant drug(s), concomitant disease(s) is clear.
- Possible: An event that might be due to the use of the study device. An alternative explanation - e.g., concomitant drug(s), concomitant disease(s) - is inconclusive. The relationship in time is reasonable; therefore, the causal relationship cannot be excluded.

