The seriousness of an AE or ADE will be preliminarily determined by study clinicians, but final determination will be provided by an independent external clinician to eliminate bias in classification. All AEs must have their relationship to the investigational devices assessed by an external clinician based on the temporal relationship and his/her clinical judgment. The study clinicians and Medical Expert will be responsible for determining whether an ADE is expected or unexpected. An ADE will be considered unexpected if the nature, severity, or frequency of the event is not consistent with the risk information previously described for the study intervention.

All AEs, ADEs, and complaints will be recorded. The external clinician and the Medical Expert will determine whether it is in the participant's best interest to remain in the study after any serious AE or UADE and notify the PI accordingly.

Study PIs will report UADEs to the IRB and DSMB within 10 working days. Limbix will immediately conduct an evaluation of any reported UADEs and will report such effects to the FDA within 10 working days. If it is determined that an UADE presents an unreasonable risk to subjects, the investigation or parts of the investigation presenting that risk will be terminated as soon as possible. Termination shall occur not later than 5 working days after the sponsor makes this determination and not later than 15 working days after the sponsor first receives notice of the effect. Limbix will not resume a terminated investigation without IRB approval and, if the investigation was terminated under paragraph (b)(2) of 21 CFR 812.46, FDA approval.

Per 21 CFR 56.108(b)(1) and 21 CFR 812.150(a)(1), PIs will report any unanticipated problem involving risk to human subjects or others to the IRB no later than 10 business days from the time of identification. An unanticipated problem must meet all the following criteria:

- Unexpected (in terms of nature, severity, or frequency) given the information provided in research-related documents and the characteristics of the subject population being studied;
- Related or possibly related to participation in the research; AND
- Suggests that the research places subjects or others at a greater risk of harm than was previously

known or recognized.

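### The Participant Symptom Check feeds the adverse-event outcome, but it has no baseline administration, no stated anchor for its first recall window and no new-or-worsened rule, so symptoms that pre-date randomisation may be counted as AEs

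*Combined protocol and SAP*

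**What the plan says.** Section 3.4 describes the PSC, completed by participants and, for those under 18, by guardians, as covering "negative symptoms and changes in treatment since the last check-in", with multiple-choice and free-text answers. Table 1 in the same section marks both PSC rows at the weekly, post-intervention and 1-month columns. Eligibility Screening and Baseline are blank.

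Section 4.5 makes the PSC a source for the main safety outcome. That outcome is "Number of adverse events (AEs), number of participants with AEs, and rates of AEs based on" PHQ-8 deterioration and the weekly PSC answers, in both groups.

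Section 4.8 says "An adverse event is defined as any unwanted medical occurrence that occurs during the study". It adds that "All AEs must have their relationship to the investigational devices assessed by an external clinician based on the temporal relationship" and on clinical judgment.

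On who is enrolled, section 2.6 excludes a suicide attempt in the past year and active ideation with intent, but not earlier or milder suicidality. Section 3.1 says "Participants who report a history of suicidal ideation or self-harm urges will be prompted to complete a safety plan". Section 4.8 lists suicidal ideation, self-injury ideation and non-suicidal self-injury among the anticipated AEs.

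**The concern.** An AE table is useful when it shows what arose or worsened after allocation. Some of the symptoms that this trial expects to record as AEs may already be present at entry. A participant whose ideation is the same before and after randomisation can report it at the first weekly PSC, and the plan gives no matched earlier answer to compare it with and no rule for classifying it.

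Two uses of the data are affected. The first is the between-arm display of AEs: a common background of long-standing symptoms makes the arms look more alike in ratio terms and makes the difference less precise. The second is the external clinician's causality rating, which leans on timing. Device effects can be assigned only in the SparkRx arm (section 4.8), so whether a symptom pre-dated the app matters most there.

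**Working it through.** **Document check**

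1. *Schedule.* In Table 1 every other repeated symptom, function or resource measure has a pre-randomisation value: PHQ-8 at screening; guardian PHQ-8, GAD-7, BADS, PQ-LES-Q, absenteeism and healthcare utilization at baseline. The PSC and its guardian proxy do not.
2. *Recall window.* Each later PSC refers back to the one before it. The first has no predecessor, and the text states no other starting point. The gap is therefore sharpest at the first check, although a persisting symptom can be reported again later.
3. *AE rule.* The definition requires occurrence during the study. It does not require onset after randomisation or worsening from baseline. The only allowance for pre-existing conditions concerns planned hospitalization. Sections 4.7.1 to 4.7.5 contain no safety analysis that could supply a rule.
4. *Comparison within the plan.* In section 4.8.1 the first limb of PHQ-8 deterioration requires a rise from baseline. The PSC stream has no equivalent. (The second limb, a high score at two consecutive timepoints, states no change from baseline either; that is a separate matter.)
5. *Other pre-randomisation data.* History of ideation or self-harm urges (3.1), medical history and medications (3.4), PHQ-8 and GAD-7 are available. None is shown to correspond item by item to the PSC. For the suicidality history the text gives no recall period or severity, so it does not show whether ideation reported in week 1 is unchanged, worse or new.

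**Illustration of size**

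The plan gives no AE rates, so there is no figure to reproduce. The inputs below are assumptions, except for 110 per arm (220 enrolled, 1:1).

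- p = share in each arm with a PSC-reportable symptom at entry: 15%, range 5% to 30%.
- r = risk of a new event among the rest: 5% (eUC), 10% (SparkRx).
- All pre-existing symptoms counted: share with an AE = p + (1 − p)r.
- Only new events counted: (1 − p)r.
- Difference between arms under either rule: (1 − p)(0.10 − 0.05), because p cancels.
- SE of the difference = √{[a(1 − a) + b(1 − b)]/110}, where a and b are the two shares.

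For p = 0.15, all counted: eUC 0.15 + 0.85 × 0.05 = 0.1925; SparkRx 0.15 + 0.85 × 0.10 = 0.235; ratio 1.22; difference 0.0425; SE = √[(0.1554 + 0.1798)/110] = 0.055. New only: 0.0425 v 0.085; ratio 2.0; difference 0.0425; SE = √[(0.0407 + 0.0778)/110] = 0.033.

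| p | All counted, eUC v SparkRx | Ratio | New only | Ratio | Difference, both rules | SE, new only → all counted |
|---|---|---|---|---|---|---|
| 5% | 9.75% v 14.5% | 1.49 | 4.75% v 9.5% | 2.0 | 4.75 points | 3.5 → 4.4 points |
| 15% | 19.25% v 23.5% | 1.22 | 4.25% v 8.5% | 2.0 | 4.25 points | 3.3 → 5.5 points |
| 30% | 33.5% v 37% | 1.10 | 3.5% v 7% | 2.0 | 3.5 points | 3.0 → 6.4 points |

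*Sensitivity.* The model lets no one with a pre-existing symptom have a new event. If they could, at the same r, a new-or-worsened count would give 5% v 10%, a difference of 5 points. Counting everything would still give 4.25 points at p = 15%. The loss is 5 × p points: 0.25 at p = 5%, 0.75 at 15% and 1.5 at 30%.

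**The case against.** The best defence is that PSC answers do not become AEs automatically. Under section 4.8.1, staff review them daily and pass safety concerns to a study clinician. The Medical Expert makes an initial classification, and an independent external clinician makes a separate one that prevails. The AE definition requires occurrence during the study, the causality scale considers concomitant disease as well as timing, and nothing says that the clinician lacks the participant's history. This stands against two stronger readings that a reader might infer:

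- *That pre-existing symptoms are counted as AEs.* No section says so. The plan leaves it open, and they may be.
- *That old and new symptoms cannot be separated at all.* The pre-randomisation data listed above, including the suicidality history, allow some separation. It is incomplete, not impossible.

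It can also be said that the PSC wording is in Appendix 1, which is not in the text reviewed. A first-check anchor or new-or-worse wording may exist there. That would narrow the point, but an anchor alone supplies neither a baseline answer nor a counting rule.

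Section 4.7 defers detail to a later SAP, and a new-or-worsened definition could be placed there. A baseline answer that was never collected cannot be recovered by an SAP.

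Finally, section 4.7 specifies no between-arm AE test or ratio, so no planned test is distorted. The counts and rates in section 4.5 would still be read side by side.

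**Conclusion.** The gap is real and moderate in weight. The PSC feeds the AE outcome without a pre-randomisation record, a stated anchor for its first window or a new-or-worsened rule. Symptoms that pre-date randomisation may be counted as AEs and cannot be reliably separated from new ones, and the external clinician judges timing without a matched pre-device record.

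On the assumed rates, a ratio of 2.0 would read between 1.49 and 1.10 as the pre-existing share goes from 5% to 30%, with a less precise difference. This assumes that every such symptom is counted, that the share is equal in the two arms and that reporting is equal. It is a range under assumptions, not a forecast.

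A reader might infer that the omission biases the safety comparison against one arm or removes a true difference. The documents do not support that. With 1:1 randomisation the excess falls on both arms, and under the main model the absolute difference is the same whichever way events are counted. What is lost is the ratio and precision.

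**What to change.** - **Table 1 (3.4):** add the PSC, and the guardian proxy for participants under 18, to the Baseline column, completed in the portal before randomisation.
- **PSC wording:** give the baseline form a fixed recall window in place of the reference to a previous check-in (for example the past week, as BADS and PQ-LES-Q use); otherwise it would have the same gap. Anchor the first weekly PSC to the baseline session.
- **Section 4.5:** tabulate PSC-based AEs by arm as new or worsened relative to the baseline PSC, and list pre-existing symptoms separately. Because the answers are multiple-choice and free text with no severity scale described, state how worsening is to be judged.
- Clinical review of every response stays as it is.

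Cost: a few extra minutes per participant and guardian at baseline, and one derived flag.

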4.1 Primary Outcome

- The primary outcome measure is depressive symptom severity (PHQ-8 score), which will be used to compute differences in mean depressive symptoms between participants randomized to the SparkRx condition and those randomized to the eUC condition at post-intervention (5 weeks). PHQ-8 score will also be used to determine whether there is clinically-meaningful reduction in severity in the SparkRx group at post-intervention. Clinically-meaningful reduction in severity is defined as a 5 point or greater decrease in PHQ-8 score from baseline.

4.2 Secondary Outcomes

- Intervention response at post-intervention (50% reduction in PHQ-8 score from baseline)
- Remission at post-intervention (PHQ-8 score < 5)
- Clinically-meaningful reduction in severity at post-intervention (≥5 point reduction in PHQ-8 score from baseline)

